 - i. Patients provisionally enrolled based on verbal consent
 - ii. Enrollment and official consent are upon initial patient encounter with their PCP
- b. Follow-up from October 1, 2020-September 15, 2024
- c. Index Date (T0)
 - i. Initial Patient Encounter with their PCP (e.g., visit, secure message) following receipt of packet
- d. Follow-up Period – Analyze two time points
 - i. 6 months following the index date (T6)
 - 1. Follow-up survey may be more than six months after the initial visit, depending on when the RAs are able to successfully contact the patient for the follow-up survey
 - ii. 12 months following the index date (T12)

3. **Study Arms**

- a. Study Arm Assignment
 - i. PCPs were randomized upon Academic Detailing session attendance
 - ii. Patients were assigned to a study arm based on their PCP on file upon enrollment
- b. Arm 1 (Control): Academic Detailing + General Packet
- c. Arm 2 (Intervention): Academic Detailing + Patient Pre-Visit Preparation Packet

Statistical Analysis Plan (SAP)

We will construct generalized estimating equation (GEE) models to compare changes from baseline in clinical and patient-reported outcomes ($p < 0.05$) between clinical trial arms. All statistical analyses will use SAS 9.4 (SAS Institute Inc), and regression models were fit using PROC GENMOD. For each deprescribing, patient-reported and hypoglycemia-related outcome, we will construct a regression model with baseline measurements of the outcome included as covariates and a repeated statement to account for patient clustering within PCP panels. We will also examined heterogeneity of treatment effect (HTE) based on demographic and baseline clinical variables by calculating interaction term p-values from the models with and without interaction terms at 6 and 12 months for the deprescribing primary outcome.

The Table lists each baseline covariate that will be used in each outcome model.

Outcome Model	Baseline Covariate(s) Included
Any deprescribing (T6 and T12 models)	On insulin at T0 – y/n and on sulf at T0 – y/n
Self-reported severe hypoglycemia event from T6 patient survey	Self-reported severe hypoglycemia event from T0 patient survey
Hypoglycemia-related ED or IP diagnosis (T6 and T12 models)	Hypoglycemia-related ED or IP diagnosis in 1 year prior to T0
HbA1c lab result (T6 and T12 models)	Latest HbA1c lab result prior to T0 >8%

4. Outcomes

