Outcome	Timepoints	Summary Statistic in Each Arm and At Each Timepoint	Effect Estimate, Difference in:	Initial Statistical Test
HbA1c Value	Baseline, Follow-up	Mean and CI	Means	T-test
HbA1c <=8	Baseline, Follow-up	% of Arm	Proportions	Chi-sq
Hypo IP	Baseline, Follow-up	% of Arm	Proportions	Chi-sq
Hypo ED	Baseline, Follow-up	% of Arm	Proportions	Chi-sq
ED	Baseline, Follow-up	% of Arm	Proportions	Chi-sq
IP	Baseline, Follow-up	% of Arm	Proportions	Chi-sq
PCP Visits	Baseline, Follow-up	% of Arm	Proportions	Chi-sq
Survey Responses	Baseline, Follow-up	% of Arm	Proportions	Chi-sq
PEPPI Scores	Baseline, Follow-up	Mean and CI	Means	T-test
PAID5 Scores	Baseline, Follow-up	Mean and CI	Means	T-test
RAND PSQ	Follow-up	% of Arm	Proportions	Chi-sq

a. Primary Outcomes

- i. Deprescribing of either insulin or SU
 - 1. Discontinuation of either insulin or SU
 - 2. Reduction in dose of insulin or SU
 - 3. Switch from a higher risk to lower risk version of insulin
- ii. Timeframe for determining baseline and follow-up medication regimen
 - 1. Single-date regimen at T0, T6, and T12

b. Secondary Outcomes

- i. Changes in HbA1c levels
 - 1. Baseline HbA1c: Use most recent prior to T0 in the year prior to T0; if no HbA1c in year prior to T0, pull forward eligibility HbA1c
 - 2. Follow-up T6: in this timeframe, pick the HbA1c closest to T6
 - 3. Follow-up T12: in this timeframe, pick the HbA1c closest to T12?
- ii. Hypoglycemic-related hospitalizations
- iii. Hypoglycemic-related ED visits
 - 1. Number of hypoglycemic-related ED visits between T0-T6

c. Patient-reported outcomes (Change between baseline and follow-up questionnaires)

- i. Incidence of patient-reported moderate and severe hypoglycemic events
- ii. Less diabetes-related stress
- iii. Perceived quality of care

5. **Baseline data**

- a. PCP Data
- b. Patient Data
 - i. Demographics: Race, Ethnicity, Age, Gender, Language
 - ii. Patient Engagement: Kp.org status, Kp.org usage
 - iii. Comorbidities Data lookback: 1 year before study visit date
 - iv. Clinical Characteristics
 - 1. Medications: Diabetes Medication Regime (Insulin, Sulfonylurea), Medication Count (All Medications)
 - 2. Labs: HbA1c
 - a. Data lookback: 1 year before study visit date
 - b. HbA1c Selection: most recent one prior to T0
 - 3. Hypoglycemic-related hospitalizations
 - 4. Hypoglycemic-related ED Visits
 - v. Membership/Insurance
 - vi. Baseline Survey Responses

6. **Lost to Follow-up**

- a. Reasons

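### Hypoglycemia ED visits are defined as a number but analysed as a proportion, and the frequent visit outcomes have only an unclustered chi-square on a percentage

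*Combined protocol and SAP*

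**What the plan says.** Section 4.b.iii.1 defines the hypoglycemia ED outcome as "Number of hypoglycemic-related ED visits between T0-T6". It is the only visit outcome worded as a number.

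The outcome table at the start of Section 4 treats it differently: "Hypo ED Baseline, Follow-up % of Arm Proportions Chi-sq". Hypoglycemia IP, all-cause ED, all-cause IP and PCP visits have the same layout, for example "PCP Visits Baseline, Follow-up % of Arm Proportions Chi-sq". No threshold is given, so any-versus-none is the natural reading. The last column is headed "Initial Statistical Test".

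The Statistical Analysis Plan section says: "For each deprescribing, patient-reported and hypoglycemia-related outcome, we will construct a regression model with baseline measurements of the outcome included as covariates". A repeated statement handles clustering within PCP panels. The model table has one row for hypoglycemia visits, "Hypoglycemia-related ED or IP diagnosis (T6 and T12 models", whose covariate is "Hypoglycemia-related ED or IP diagnosis in 1 year prior to T0". No distribution, link or offset is named, and there is no row for all-cause ED, IP or PCP visits.

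Under Study Arms (3.a), PCPs are the units randomised and patients take the arm of their PCP. T0 (Section 2.c) is "Initial Patient Encounter with their PCP (e.g., visit, secure message) following receipt of packet", and follow-up runs to 6 and 12 months after it.

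**The concern.** Two things are at stake.

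First, a listed secondary outcome has no analysis that matches its definition. A number of visits, a percentage of patients with any ED visit, and a percentage with an ED or inpatient diagnosis are three different quantities. As written, the analyst could report any of them, and could choose after seeing the data.

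Second, all-cause ED, IP and PCP visits have only one test assigned to them by name: a chi-square on patients. It takes no account of PCP as the randomised unit, although the SAP does so for its models. It also reduces each patient's visits to one yes/no value. When most patients have several visits, nearly everyone is a yes, and the test cannot see a change in how often they come. The intervention prepares patients for PCP visits, so PCP contact is a natural place to look for an effect.

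**Working it through.** **Step 1: the passages side by side, hypoglycemia ED visits.**

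| Place | Quantity | Analysis |
|---|---|---|
| 4.b.iii.1 | Number of visits, T0 to T6 | None stated |
| Outcome table | Percentage of arm | Difference in proportions, chi-square |
| SAP model table | ED or IP diagnosis, apparently yes/no | GEE clustered by PCP |

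No row analyses a number.

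**Step 2: information kept by any-versus-none.** The documents give no sample size, visit rate, dispersion or power, so there is no figure to reproduce and every mean below is an assumption. Let m be the mean visits per patient and k the negative binomial dispersion. For a log rate ratio near zero, the share kept relative to the count is

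- Poisson: m / (e^m − 1)
- Negative binomial: [d² / (p0(1 − p0))] / [m / (1 + km)], with p0 = (1 + km)^(−1/k) and d = m(1 + km)^(−1/k − 1). At k = 1 this reduces to 1/(1 + m).

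| Assumed m | Poisson | k = 0.5 | k = 1 | k = 2 |
|---|---|---|---|---|
| 0.05 | 97.5% | 96.4% | 95.2% | 93.1% |
| 0.2 | 90.3% | 86.6% | 83.3% | 78.0% |
| 0.5 | 77.1% | 71.1% | 66.7% | 60.4% |
| 2 | 31.3% | 33.3% | 33.3% | 32.4% |
| 3 | 15.7% | 22.9% | 25.0% | 26.0% |
| 4 | 7.5% | 16.7% | 20.0% | 22.2% |

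At means of 2 to 4 the loss is 67% to 93%. Half is lost at m = 1.26 (Poisson), 1.12, 1.00 and 0.81 (k = 0.5, 1, 2).

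**Step 3: what that does to power.** Assumed: 250 per arm, rate ratio 1.3, two-sided 0.05, clustering ignored for both tests. The proportion uses the pooled two-proportion z-test with p = 1 − (1 + km)^(−1/k). The count uses Var(log rate) = (1/m + k)/n in each arm.

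Example, m = 3 against 3.9, k = 0.5:
- Proportions: 1 − 2.5^(−2) = 0.840 and 1 − 2.95^(−2) = 0.885. Difference 0.0451, standard error 0.0308, z = 1.465; power = Φ(1.465 − 1.96) = 31%.
- Count: variance (0.8333 + 0.7564)/250 = 0.00636, standard error 0.0797; z = 0.2624/0.0797 = 3.29; power = Φ(3.29 − 1.96) = 91%.

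| Assumed outcome | k | Any-versus-none | Count |
|---|---|---|---|
| PCP visits, m = 3 | 0.5 | 31% | 91% |
| PCP visits, m = 3 | 1 | 23% | 73% |
| PCP visits, m = 2 | 0.5 | 38% | 86% |
| PCP visits, m = 2 | 1 | 27% | 69% |
| All-cause ED, m = 0.4 | 0.5 | 33% | 43% |
| All-cause ED, m = 0.4 | 1 | 27% | 37% |
| Hypoglycemia ED, m = 0.05 | 1 | 9.7% | 10.0% |
| Hypoglycemia ED, m = 0.02 | 1 | 6.3% | 6.4% |

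The pattern is the same with other assumptions (Poisson, 200 per arm, rate ratio 0.75): 8.5% against 8.6% at m = 0.05, 39% against 47% at m = 0.5, and 55% against 99.6% at m = 3.

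**Step 4: the windows.** The history covariate covers one year and the T6 outcome six months. A constant 6% yearly risk (assumed) gives 1 − √(1 − 0.06) = 3.05% over six months with no effect. Both arms share the same windows, so this touches only a within-arm, before-and-after reading.

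**The case against.** The strongest reply is that the large loss falls where it matters least. The one outcome called a number is probably rare, and for it the choice hardly changes power. PCP visits appear only in the outcome table, not among the primary or secondary outcomes, and a patient-level proportion is a legitimate target. Chi-square is labelled an initial test, and hypoglycemia visits also get a clustered GEE. The SAP's opening sentence on GEE refers to clinical outcomes generally, which could be stretched to cover all-cause visits. Most of this stands and limits the importance of the point. It does not supply an analysis for the stated number of visits. Nor does it give all-cause ED, IP or PCP visits a named clustered model: the sentence on which outcomes are modelled and the model table both omit them.

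A reader might also infer more than the documents support:

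- **All visit outcomes are counts whose information is mostly discarded.** Only hypoglycemia ED visits are worded as a number, and for that outcome any-versus-none is close to fully efficient.
- **The PCP-visit percentage is saturated because everyone has an encounter at T0.** T0 may be a secure message, and follow-up is described as the time after T0. A forced 100% needs T0 to be counted and messages to count as visits, and neither is stated. At m = 3 the assumed control percentages are 84% (k = 0.5) and 75% (k = 1), below a ceiling.
- **The one-year and six-month windows bias the comparison of arms.** They do not. A covariate need not share the outcome's time scale, and the one-year lookback is stated for the model, not for the table row.

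**Conclusion.** The mismatch in the hypoglycemia ED outcome is established by reading and needs to be reconciled. Its effect on power is negligible at the assumed means of 0.02 to 0.05; what is at issue there is which quantity will be reported.

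For all-cause ED, IP and PCP visits, the only named test ignores the randomised unit. The documents give no intracluster correlation or panel size, so the size of that error cannot be stated. The any-versus-none form costs about two thirds or more of the information if PCP visits average 2 to 4 per six months. It costs about 10% to 40% for all-cause ED or IP at means of 0.2 to 0.5. These figures rest on assumed means and dispersion, and the power figures also on assumed sample sizes and rate ratios, with clustering left out.

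The outcomes concerned are secondary or table-only. The change is worth making because it is cheap; no primary outcome is affected.

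**What to change.** - **PCP visits, all-cause ED visits and IP stays:** analyse the counts with a negative binomial or robust Poisson GEE clustered by PCP, with log observed person-time as offset and the baseline rate per person-time as covariate. The offset also handles follow-up cut short by death or loss of membership (Section 6). Keep the percentages as description.
- **Windows:** count from the day after T0. State the baseline window for each visit outcome and whether secure messages count as PCP visits.
- **Hypoglycemia ED visits:** keep the clustered ED-or-IP model as the main analysis and state that it is yes/no. Report the number of ED visits as a rate with robust Poisson errors, so that 4.b.iii.1 has an analysis, and bring the outcome table into line.

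The cost is a few lines of SAP text and a different distribution option in PROC GENMOD, which the plan already uses; the counts should be in the same utilisation records. The downside is that sparse counts can give unstable fits and a few frequent users can influence a rate. That is why the yes/no model stays the main analysis for hypoglycemia and the percentages stay beside the rates. The plan is dated after the stated end of follow-up, so the revision should say whether results by arm had been seen when it was made.

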 - i. Loss of membership during study period
 - ii. Death
 - iii. PCP Switches

7. **Analyses**

- a. Comparison of baseline characteristics between intervention and control
- b. Comparison of consented vs declined
 - i. Characteristics as of Eligibility Date:
 - 1. Demographics: gender, age, race, ethnicity, language
 - 2. Study eligibility data: HbA1c, INS/SU Y/N
- c. Flow through the study
 - i. Time from provisional enrollment to actual enrollment
 - ii. Reasons for drop out and missing data
- d. Comparison of outcomes between intervention and control
 - i. Analysis of subsets of patients based on specific characteristics

8. **Final Analytic Tables**

- a. Enrolled vs Declined
- b. Table 1-Intervention vs Control
- c. PCP Table
- d. Outcomes table

9. **Sensitivity Analysis**

- a. Sensitivity analyses to assess the impact of missing data
- b. Sensitivity analyses based on modality of visit (virtual vs. in-person)
- c. Strata of people who had prior hypoglycemic events

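### Section 6 counts a PCP switch as loss to follow-up without limiting it to switches before T0, and nothing says that later switchers stay in the models or in which GEE cluster

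*Combined protocol and SAP*

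**What the plan says.** Section 6 lists three reasons for loss to follow-up: "Loss of membership during study period", death, and the entry "iii. PCP Switches". The last has no timing and no statement of what follows from it.

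The relevant dates are in Section 2. T0 is the "Initial Patient Encounter with their PCP (e.g., visit, secure message) following receipt of packet", and item a.ii adds: "Enrollment and official consent are upon initial patient encounter with their PCP". A patient is therefore fully enrolled only at T0, by which time the packet has arrived.

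Section 3.a says that PCPs were randomised and that a patient takes the arm of the PCP on file at enrollment. The SAP text fits GEE models with a repeated statement for clustering by PCP panel.

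The deprescribing outcome in Section 4.a is read from a "Single-date regimen at T0, T6, and T12". Section 7.c reports the "Time from provisional enrollment to actual enrollment" and the "Reasons for drop out and missing data". Section 9.a promises "Sensitivity analyses to assess the impact of missing data", with no method given. No section defines an analysis set or states an as-assigned or intention-to-treat rule.

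**The concern.** Death and loss of membership plausibly end data capture. A change of PCP within the health plan does not obviously do so. If the Section 6 label is applied to someone who switches after T0, outcomes that should be obtainable, including deprescribing, are set aside because of something that happened after randomisation and after the packet was delivered. The arms differ in a handout meant to change how patient and PCP interact, so switching could differ by arm, although nothing in the documents shows that it does. Two analysts working from this plan could reach different denominators for the primary outcome and different cluster assignments.

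**Working it through.** **Text check.** The plan states no figure on this point, so the first step is to take the two timings in turn.

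1. *Switch before T0.* Consent and T0 both need an encounter with the PCP. A switch at this stage can leave a patient with no T0 and hence no T6 or T12. Calling this attrition is reasonable, and Section 7.c.i follows this stage.
2. *Switch after T0, membership continuing.* Loss of membership has its own line, so the switch line must cover people who remain members. The regimen is read on fixed dates, HbA1c is a laboratory result, and the ED and inpatient outcomes are diagnoses. Nothing ties any of these to the PCP at assignment. The follow-up survey depends on when research assistants reach the patient (Section 2.d). These outcomes should therefore be obtainable, subject to confirmation of the data source.
3. *Arm.* Section 3.a.ii fixes the arm by the PCP on file, so a later switch should not move a patient between arms.
4. *Retention and cluster.* No section covers either.

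**Illustration of size (assumptions only).** The documents give no sample size, switching rate or deprescribing rate. Let s be the share of an arm switching after T0 and d the stayer-minus-switcher deprescribing rate, with 1 = intervention and 0 = control. An arm's as-assigned rate equals its stayers' rate minus s × d. Hence

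stayers-only difference − as-assigned difference = s1 × d1 − s0 × d0.

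Assume s from 0.05 to 0.15 and d from −0.10 to +0.10.

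- Same gap in both arms: (s1 − s0) × d. The largest value is (0.15 − 0.05) × 0.10 = 0.010, or 1.0 point in either direction. It is zero if s1 = s0.
- Switchers like stayers (d1 = d0 = 0): zero.
- Gaps of the same sign, or one of them zero: the largest value is 0.15 × 0.10 − 0.15 × 0 = 0.015, or 1.5 points. With 10% switching in both arms and gaps 5 points apart, it is 0.10 × 0.05 = 0.005, or 0.5 point.
- Gaps of opposite sign: the extreme is 0.15 × 0.10 − 0.15 × (−0.10) = 0.030, or 3.0 points. Anything above 1.5 points needs opposite signs.

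**Precision.** With independent patients, losing 5% multiplies the standard error by 1/√0.95 = 1.026, and losing 15% by 1/√0.85 = 1.085. Positive within-PCP correlation makes these smaller. Assume 20 patients per PCP and an intracluster correlation of 0.05, and use (1 + (m − 1) × ICC)/m for the variance per panel:

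- full panel, m = 20: (1 + 19 × 0.05)/20 = 1.95/20 = 0.0975;
- 15% lost, m = 17: (1 + 16 × 0.05)/17 = 1.80/17 = 0.1059;
- ratio 1.086, square root 1.042, so an increase of about 4.2% rather than 8.5%.

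**The case against.** The strongest reply is that Section 6 is only a list of labels for a flow diagram. It is headed as reasons, and Section 7.c.ii reports reasons for dropout under study flow. Follow-up also opens on October 1, 2020, the day provisional enrollment opens, so the list may be meant for losses between provisional enrollment and T0. Patients lost there have no T6 or T12 outcome to discard.

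Much of this stands. A reader might infer that the plan removes switchers from the models. It does not say so; exclusion is what the label implies if taken literally. A reader might also take Section 6 as the only text bearing on switchers. It is not, because Section 3.a.ii already ties the arm to the PCP on file, and the open questions are retention and cluster. Finally, the size rests wholly on assumed inputs.

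What does not stand is the conclusion that nothing needs changing. The pre-T0 reading is possible but unstated, loss to follow-up ordinarily means that no outcome is available, and no other section overrides it. Section 9.a does not help: a missing-data sensitivity analysis is no substitute for using outcomes that exist.

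**Conclusion.** The point holds as a gap with a concrete remedy. Section 6 does not separate pre-T0 from post-T0 switches, and the plan neither states that later switchers are retained nor assigns them a cluster. Dropping them would lose precision and condition on a post-randomisation event.

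The size and direction of any bias cannot be derived from the documents. On the assumed ranges it is at most 1.0 point with a common gap and zero if switching is also equal by arm. The 3.0-point corner should not be read as an expected bias, since it needs maximal switching and 10-point gaps of opposite sign, which nothing in the documents suggests. The 2.6% to 8.5% increase in standard error ignores clustering and overstates the loss if within-PCP correlation is positive. That outcomes remain obtainable after a switch is an inference that the sponsor should confirm.

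The Protocol Summary's wording on whether patients or PCPs are randomised is a separate matter and adds no weight here.

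**What to change.** - In Section 6, limit PCP switches as an attrition reason to those before T0 that leave no index encounter.
- State that every enrolled patient is analysed in the arm and GEE cluster of the PCP who determined arm assignment, whatever the later PCP. The sponsor should confirm whether that PCP is fixed at provisional enrollment or at the index encounter: Section 3.a.ii refers to enrollment, Section 2.a.ii places enrollment at the encounter, yet the packet precedes the encounter.
- Keep post-T0 switchers through T6 and T12 while they remain members. Use survey outcomes where collected, and treat the rest as missing under Section 9.a.
- Report the number of switches before and after T0 by arm.

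The cost is a few sentences in the SAP and, if switchers were already set aside, re-extraction of their record-based outcomes. Follow-up closed on September 15, 2024, before the plan's date of 12/2/2024, so surveys not collected from switchers may not be recoverable. The as-assigned effect may also be slightly diluted by patients who left the PCP who determined their arm.
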